### 8.2.3.2 Distant Metastasis-Free Survival (DMFS)

DMFS will be analyzed using the same methods described for OS/PFS. In the event that the percent of subjects with competing events such as death, lost to follow-up and withdrawal of consent in either arm exceeds 3%, the cumulative incidence estimates and Gray's test will be the main DMFS comparison between the treatment arms.

### 8.2.3.3 Objective Response Rate (ORR)

ORR will be estimated using the ITT set and EE set by both investigator's and IRC response assessment, the percent of subjects will be provided along with their corresponding 2-sided the 95% exact CI using Clopper-Pearson method. Also the best overall tumor response (CR, PR, SD, PD and not evaluable) will be tabulated with 2-sided 95% CI in the same table.

Also, ORR will be compared between treatment arms using a logistic regression. Logistic regression will be performed with the treatment arm and all stratification factors as independent variables. Treatment arm will be compared using the likelihood ratio chi-square test.

### 8.2.3.4 QoL using the EQ-5D-5L or EQ-5D-Y

QOL analysis will be performed based on the ITT and EE set.

For EQ-5D-5L, number of subject and percentage will be provided by visit for each dimensions; observation, change and % change from baseline will be summarized for EQ-5D index value and VAS by each scheduled visit per treatment arm and overall.

Also, the treatment difference between CMB305 to placebo in the mean and change of the EQ-5D-5L index score/VAS from baseline to each post baseline analysis visit will be estimated using pattern mixture models. The following covariates will be considered: randomization stratification factors, baseline value of index score/VAS, treatment arm, analysis visit, analysis visit \* treatment arm. Both index score/VAS values and change from baseline of each analysis visit will be included as dependent variable separately.

EQ-5D-Y will be analyzed using the same methods described for EQ-5D-5L, except for index score (no index score will be calculated for EQ-5D-Y).

Example code for mixed model for repeated measures for change from baseline of index score/VAS:

```
proc mixed data = data.q01 method=REML;
  class subjid trt avisit stratum1 stratum2 stratum3;
  model socre_change = baseline stratum1 stratum2 stratum3 trt avisit
trt*avisit
  /NOINT SOLUTION DDFM=SAT;
  repeated avisit/ type = UN subject = subjid r;
  Lsmmeans trt*avisit/diff CL;
run;
```

In the case of non-convergence, the covariance structure type and computation method will be adjusted until convergence achieves without errors.

## 8.2.4 Analysis of Exploratory Efficacy Variables

The baseline anti-NY-ESO-1 immune response and histologic and molecular changes in peripheral blood and tumor tissue and their association with clinical outcomes will be explored. In addition, a relationship between an induced anti-NY-ESO-1 immune response as well as tumor tissue changes during study treatment and clinical outcomes will be evaluated using peripheral blood and tumor tissue biopsies collected during study treatment at select sites.

## 8.3 Safety Analyses

All analyses for the safety evaluation variables will be performed on safety set by treatment arm and overall.

Baseline is defined as the last non-missing value prior to the first dose date on day 1, unless otherwise noted.

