- ^b In the Boost Phase, tumor imaging will be performed every 8 weeks for 1 year or until investigator-determined progressive disease, using RECIST v1.1, is documented.
- ^c The Post-treatment period will begin at the end of treatment and will continue until investigator-determined progressive disease, using RECIST v1.1, is documented. If a subject has reached 12 months on study without disease progression, tumor imaging will be performed every 12 weeks ±7 days until disease progression.
- ^d The Long-term Follow-up period will begin at the time investigator-determined progressive disease (using RECIST v1.1) is documented and will continue for up to 5 years, until the date of death, or until sponsor notification of study closure.
- ^e The following information must be available at Day 1: subjects must have documented completion of first-line systemic anti-cancer therapy and must have received at least 4 to 8 cycles of therapy (or no more than 180 days of systemic anti-cancer therapy); results of IHC testing for the presence of NY-ESO-1 (≥1% expression) must be available from the central laboratory; and the investigator-evaluated tumor response, using RECIST v1.1, to first-line systemic anti-cancer therapy must be documented.

- ^f During the study dosing period, all laboratory assessments are to be performed prior to dosing. Hematology and clinical chemistry samples will be shipped to the central laboratory for safety analyses, and will include: chemistry with liver function tests, lactate dehydrogenase, alkaline phosphatase, albumin, thyroid function, and hematology with complete blood count with differential. Urinalysis will be conducted at the central laboratories. All laboratory tests to be performed are listed in [Table 4](#).
- ^g Blood for anti-NY-ESO-1 T cell assessments to be collected only for subjects on prior to dosing on Day 1 and Day 92 only at select US sites. Additional blood samples for immunity assessments will be drawn for any subject who has no evidence of tumor progression by RECIST v1.1 at 1 year at the same select US sites.
- ^h For circulating tumor genomics, please see lab manual.

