3.3 Study Duration and Dates

Subject participation is inclusive of the Pre-screening, Screening, Treatment, Post-treatment, and Long-term Follow-up periods.

The Pre-screening period is up to 151 days (Day -180 to Day -29) and begins from the time the subject and/or their legally authorized representative sign the Pre-screening ICF/assent form to the time the Main Study ICF/assent form is signed. The Pre-screening period can start as early as the first dose of first-line systemic anti-cancer therapy.

The duration of the Screening period is 28 days (Day -28 to Day -1) and begins on the date the subject and/or their legally authorized representative sign the Main Study ICF/assent form and ends at time of randomization. The screening window may be extended up to 56 days by the sponsor, if a patient is recovering from toxicity related to first line systemic anti-cancer therapy, or completing local regional therapy, or baseline imaging needs adjudication to determine eligibility.

The Treatment period will begin on the day of randomization (Day 1), which is to be within 28 days after the last dose of first-line systemic anti-cancer therapy or the last day of local regional therapy, if applicable, and will continue until investigator-determined radiographic PD

(using RECIST v1.1) is documented, the occurrence of unacceptable toxicity, or until 1 year after the first dose, whichever occurs first. All visits during the Treatment period will have a window of ± 3 days from the day specified.

The Post-treatment period (for subjects who discontinue study treatment for reasons other than disease progression) will begin at the end of treatment and will continue until investigator-determined PD (using RECIST v1.1) is documented. All visits during the Post-treatment period will have a window of ± 7 days from the day specified.

The Long-term Follow-up period will begin at the time investigator-determined PD (using RECIST v1.1) is documented and will continue for up to 5 years, until the date of death, or until sponsor notification of study closure. All visits during the Long-term Follow-up period will have a window of ± 14 days from the day specified.

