f Obtain and review images (CT or MRI) collected at the standard-of-care time point for the first evaluation of response to first-line systemic anti-cancer therapy. The subject's response to first-line systemic anti-cancer therapy will be assessed by the investigator using RECIST v1.1 and documented in the eCRF.

g Tumor imaging (CT or MRI) will be performed after completion of the planned 4-cycles to 8-cycles of first-line systemic anti-cancer therapy for the evaluation of response at baseline, as assessed by the investigator using RECIST v1.1. The images collected at this time point will serve as the baseline assessment for the efficacy evaluations. These images must be collected within 28 days after the date of last dose of first-line systemic anti-cancer therapy.

h Results from the central laboratory will be used to determine eligibility and for the safety analysis. Laboratory tests performed by the central laboratory will include: chemistry with liver function tests, lactate dehydrogenase, alkaline phosphatase, albumin, hematology with complete blood count with differential, HIV, HepB, and HepC. Coagulation samples will be drawn only at Screening and shipped to the central laboratory (prothrombin time, partial thromboplastin time, and international normalized ratio) for analysis. Urinalysis will be conducted at the central laboratory. All laboratory assessments to be performed are listed in protocol Table 4.

i The peripheral blood on all subjects must be collected Day -28 to Day -7 during Screening and will be used for plasma ELISA testing; results of the assessment will be used for stratification and randomization.

j For circulating tumor genomics, please see lab manual.

k For FCBP, serum pregnancy testing will be performed during Screening.

l Vital sign measurements will include body temperature, heart rate, respiratory rate, and resting systolic and diastolic blood pressure.

m At Screening, the physical examination should include an evaluation of organ systems, including, but not limited to, head and neck; chest and lungs; cardiac; gastrointestinal; neurologic; endocrine; and musculoskeletal and integument. Other organ systems should be evaluated as directed by medical history or current symptoms. Measurements of body weight and height will be obtained.

Table 2 Schedule of Events for the Treatment Period through Long-term Follow-up Period

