AE = adverse event; CT = computed tomography; ECOG = Eastern Cooperative Oncology Group; IHC = immunohistochemistry; MRI = magnetic resonance imaging; NY-ESO-1 = New York esophageal squamous cell carcinoma-1; QoL = quality of life; RECIST = Response Evaluation Criteria in Solid Tumors; SAE = serious adverse event

a Day 1 will occur within 28 days after the last dose of first-line systemic anti-cancer therapy or the last day of local regional therapy. Day 1 procedures must occur within 72 hours of randomization.

b In the Boost Phase, tumor imaging will be performed every 8 weeks for 1 year or until investigator-determined progressive disease, using RECIST v1.1, is documented.

c The Post-treatment period will begin at the end of treatment and will continue until investigator-determined progressive disease, using RECIST v1.1, is documented. If a subject has reached 12 months on study without disease progression, tumor imaging will be performed every 12 weeks ±7 days until disease progression.

d The Long-term Follow-up period will begin at the time investigator-determined progressive disease (using RECIST v1.1) is documented and will continue for up to 5 years, until the date of death, or until sponsor notification of study closure.

e The following information must be available at Day 1: subjects must have documented completion of first-line systemic anti-cancer therapy and must have received at least 4 to 8 cycles of therapy (or no more than 180 days of systemic anti-cancer therapy); results of IHC testing for the presence of NY-ESO-1 (≥1% expression) must be available from the central laboratory; and the investigator-evaluated tumor response, using RECIST v1.1, to first-line systemic anti-cancer therapy must be documented.

- f During the study dosing period, all laboratory assessments are to be performed prior to dosing. Hematology and clinical chemistry samples will be shipped to the central laboratory for safety analyses, and will include: chemistry with liver function tests, lactate dehydrogenase, alkaline phosphatase, albumin, thyroid function, and hematology with complete blood count with differential. Urinalysis will be conducted at the central laboratories. All laboratory tests to be performed are listed in protocol Table 4.

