## **5.2 Safety Endpoints**

### **5.2.1 Adverse Events**

A treatment-emergent adverse event (TEAE) is defined as any AE that newly appeared or worsened in severity following initiation of the study treatment administration until 30 days after last dose of the study treatment. In addition, all study treatment related AEs are treated as TEAE.

Medical Event of Interest (MEOI) is defined as selected non-serious AEs are classified as MEOIs, refer to protocol section 6.4.7.5 for more details.

Immune-mediated event --

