### **8.3.2 Clinical Laboratory Evaluations**

All laboratory values will be converted to SI units and classified as normal, low, or high based on the normal ranges of local/central lab. All gradable laboratory parameters will be graded using the NCI CTCAE v4.03 or higher. The worst post-baseline toxicity grade will be summarized for hematologic, chemistry and coagulation parameters for all gradable laboratory parameters, otherwise, the worst abnormal will be presented instead.

Standard descriptive statistics will be presented for clinical laboratory tests, at baseline, each scheduled visit and change from baseline on safety set by each treatment arm and overall.

If lab results contain symbols like “<”, “>”, “>=” or “<=”, extract the numeric value as the limit, Example: if result is “>0.1”, “0.1” will be used for analysis.

Subject listings of laboratory test results for hematology, chemistry, urinalysis, coagulation and other laboratory tests will be provided separately. Values with CTC grade as 3 or above will be flagged in the listings.

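### SAP 8.3 sets the safety baseline by the date of first dose, which can exclude Day 1 pre-dose labs and possibly ECOG; SAP 8.3.2's local/central ranges are an undeclared departure from protocol 7.8 (minor, descriptive tables only)

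*SAP*

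**What the plan says.** **Baseline.** SAP 8.3 gives one default rule for safety variables: "Baseline is defined as the last non-missing value prior to the first dose date on day 1, unless otherwise noted". The only safety variable with its own rule is vital signs, where SAP 8.3.3 takes the pre-dose reading at each dosing visit. Laboratory tests and ECOG have no exception, and the SAP does not define post-baseline.

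**Schedule.** Table 2 in both documents places central chemistry and haematology on Day 1, and footnote f says: "During the study dosing period, all laboratory assessments are to be performed prior to dosing". ECOG is also scheduled on Day 1, with no stated timing relative to the dose. Table 1 schedules the same assessments at Screening.

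**Outputs that use baseline.** SAP 8.3.2 says: "The worst post-baseline toxicity grade will be summarized for hematologic, chemistry and coagulation parameters for all gradable laboratory parameters". It also summarises change from baseline at each scheduled visit. SAP 8.3.8 plans an ECOG shift table of worst post-baseline status against baseline.

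**Laboratory source and ranges.** SAP 8.3.2 classifies all laboratory values as low, normal or high by local/central laboratory ranges. Protocol 7.8 bases the analysis of laboratory toxicities on central values and universal normal ranges. The SAP's schedule footnotes also point to the central laboratory: "Results from the central laboratory will be used to determine eligibility and for the safety analysis" (Table 1, footnote h) and "Hematology and clinical chemistry samples will be shipped to the central laboratory for safety analyses" (Table 2, footnote f). Protocol 6.4.3.1 allows local results to be collected for subjects who have adverse events. SAP 9 lets the SAP prevail over the protocol but lists no specific change.

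**The concern.** The baseline rule compares against a date, not against the act of dosing. A sample drawn on the morning of Day 1, before the injection, carries the same date as the first dose and so is not prior to that date. Two programmers could read the sentence differently and produce different grade, change-from-baseline and ECOG shift tables from the same data. On the literal reading, an abnormality present before any treatment could appear as an on-treatment finding.

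The laboratory wording raises a second reproducibility question. If all laboratory values include local results collected because an adverse event occurred, the graded tables would mix a scheduled central series with selectively obtained local values, judged against differing ranges.

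**Working it through.** The plan gives no figure to reproduce. The check traces the rule by hand and counts scheduled assessments.

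**Step 1. Apply the rule to a Day 1 pre-dose lab.** If the sample date equals the first dose date, the condition that it precede that date is false. The rule falls back to the last earlier value, normally Screening. If the Day 1 sample is dated earlier than the dose, it remains baseline. That can happen, because the first dose need not fall on the sampling date: "Day 1 procedures must occur within 72 hours of randomization" (SAP Table 2, footnote a).

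**Step 2. Age of the substitute baseline.** Screening runs from Day -28 to Day -1. With no Day 0, that is 28 to 1 days before Day 1. Protocol 3.3 adds: "The screening window may be extended up to 56 days by the sponsor". The value could therefore be up to 56 days old, but only with an approved extension and no later pre-Day-1 result.

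**Step 3. Scheduled assessments from Day 1 (Table 2).**

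| Assessment | Days | Open to misclassification | Post-baseline once fixed |
|---|---|---|---|
| Central chemistry and haematology | 1, 22, 50, 64, 92 | at most 1/5 = 20% | 5 - 1 = 4 |
| ECOG | 1, 22, 36, 50, 64, 78, 92 | at most 1/7 = 14% | 7 - 1 = 6 |
| 12-lead ECG | 92 only (otherwise Screening) | 0 | 1 |

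These are shares of scheduled visits for a subject who completes them. For a subject who stops after Day 22, the lab share is 1/2. None of these figures is a share of subjects whose result changes.

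**Step 4. When a table entry changes.** A worst grade moves only if the Day 1 value is treated as post-baseline and is worse than every later value. A change from baseline moves whenever the Screening and Day 1 values differ. Neither document gives the frequency of either event.

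**Step 5. Laboratory wording side by side.**

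| Text | Whose results | Which ranges |
|---|---|---|
| Protocol 7.8 | central | universal |
| SAP Table 1 footnote h; Table 2 footnote f | central | not stated |
| SAP 8.3.2 | all laboratory values | local/central |

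SAP 8.3.2 differs from protocol 7.8 on ranges and, through its reference to all laboratory values, on source. The footnotes name the laboratory but no ranges, so they do not contradict the range wording. They do support keeping local values out of the graded tables. The SAP cites protocol version 2.0 and the protocol supplied is 2.1 DK, but the main changes listed for 2.1 DK do not include section 7.8.

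**Step 6. Coagulation.** SAP 8.3.2 promises a worst post-baseline grade for coagulation. Table 1 footnote h has coagulation drawn only at Screening, and Table 2 has no coagulation row. No scheduled post-baseline coagulation value exists under any definition of baseline.

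**The case against.** The strongest reply is that the benign reading of SAP 8.3 is probably the intended one. Footnote f has labs drawn before dosing, SAP 8.3.3 already treats a same-day pre-dose reading as baseline for vital signs, and SAP 5.2.1 ties TEAEs to the start of treatment: "any AE that newly appeared or worsened in severity following initiation of the study treatment administration". The worst-grade and ECOG shift problem also needs two unfavourable readings at once: Day 1 must be excluded from baseline and then counted as post-baseline. This stands as evidence of intent. It does not make the sentence as written yield that result, and the SAP has no same-day or time-of-day rule for labs or ECOG.

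On ranges, local/central may mean only that each value is judged against its own laboratory's range, and SAP 9 settles any conflict with the protocol in the SAP's favour. Both points are fair. Even so, own-laboratory ranges are not universal ranges, and the departure is nowhere identified as a change.

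Three stronger inferences are tempting and are not supported:

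- A reader might infer that the SAP contradicts itself on ranges. Footnotes h and f concern whose results are used, so they can coexist with 8.3.2's range wording.
- A reader might take 20% and 14% as the proportion of subjects or results affected. They count scheduled visits and do not measure impact.
- A reader might infer that local values will enter the graded tables. The text leaves that open, but protocol 3.1.3, protocol 6.4.3.1 and the SAP footnotes all assign the safety analysis to the central laboratory.

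The entry limits (ECOG 0 or 1, organ-function thresholds) also make severe Day 1 values less likely, although the haematology limits still permit some residual abnormality after chemotherapy.

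**Conclusion.** The point holds as a minor drafting defect with two parts. First, followed as a date comparison, SAP 8.3 replaces a same-date Day 1 pre-dose lab, and possibly ECOG, with an older Screening value, and nothing keeps the Day 1 value out of post-baseline summaries. Second, SAP 8.3.2 departs from protocol 7.8 on laboratory ranges, and leaves the source open, without saying so.

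The effect is confined to descriptive laboratory and ECOG tables, under one rule for both blinded arms. TEAEs, which protocol 7.8 makes the main basis for safety, do not depend on the SAP 8.3 baseline. PFS, OS and the type I error are untouched. The first part assumes a literal date comparison and a Day 1 assessment on the dosing date; if either fails, it has no effect. The number of subjects affected cannot be estimated. The case for acting is that the written rule gives a worse result when followed and costs almost nothing to correct.

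**What to change.** In SAP 8.3, replace the baseline sentence with:

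> Baseline is the last non-missing value before the first dose of study treatment, including Day 1 pre-dose values. Day 1 laboratory and ECOG values with no recorded time are treated as pre-dose. Post-baseline means after the first dose.

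The separate vital-signs rule in 8.3.3 can stay as the noted exception.

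In SAP 8.3.2, add:

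> Grade and change-from-baseline tables use central-laboratory values with one stated range set (the universal ranges of protocol 7.8); local values are listed only.

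The SAP should identify that range set, because neither document defines it. Remove coagulation from the worst post-baseline grade table, since it is scheduled only at Screening, and list any later local coagulation results.

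The cost is a few sentences in the SAP and the matching table specifications before database lock. No protocol amendment or new procedure is needed, and reporting clinically significant local abnormalities as adverse events is unaffected.

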### 8.3.1 Adverse Events

The verbatim terms used in the eCRF by investigators to identify adverse events will be coded to a system organ class (SOC) and a preferred term (PT) using the current Medical Dictionary for Regulatory Activities (MedDRA) version 21.0 or higher. The severity of adverse events is assessed in National Cancer Institute (NCI) common toxicity criteria for adverse events (CTCAE) Version 4.03 or higher. Only TEAEs occurring from the time of the first dose through 30 days after the last dose of the study drug and medical events of interest, immune-mediated events and related AEs will be summarized, while all AEs captured in eCRF will be listed in data listings.

TEAE will be summarized by system SOC and PT, by severity, by relationship to study treatment, and by action taken. Tables will be sorted by frequency in incidence (the highest to lowest incidence in total column).

The following TEAEs will be tabulated and organized as follows:

- Overall Summary of Treatment Emergent Adverse Events
- TEAEs by system organ class and preferred term
- TEAEs by system organ class, preferred term and worst NCI CTCAE grade
- Severe TEAEs (Grade 3 or higher) by system organ class and preferred term
- SAEs by system organ class and preferred term and worst NCI CTCAE grade
- Related TEAEs by system organ class and preferred term
- Related SAEs by system organ class and preferred term
- Related TEAEs by system organ class, preferred term and worst NCI CTCAE grade
- Related SAEs by system organ class and preferred term and worst NCI CTCAE grade
- TEAEs leading to treatment discontinuation by system organ class and preferred term
- Related TEAEs leading to treatment discontinuation by system organ class and preferred term
- TEAEs classified as Medical Event of Interest (MEOI) by system organ class and preferred term
- TEAEs resulting in death by system organ class and preferred term

TEAEs will be summarized by presenting the number and percentage of subjects having at least one TEAE in each system organ class and preferred term. A subject with multiple occurrences of the same TEAE will be counted only once in the AE category.

Separate TEAE summaries will be presented by system organ class, preferred term, and maximum CTCAE (4.03 or higher) grade. A subject with multiple CTCAE grades for the same TEAE will be summarized under the maximum CTCAE grade recorded for the event.

AEs will also be listed for individual subjects, along with information regarding onset, duration, grade, relationship to the study drug, and outcome.

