7.8 Safety Analysis

Safety will be assessed primarily based on reported AEs. A TEAE is an AE with an onset on or after the initiation of study treatment, or a pre-existing condition that worsens after initiation of study treatment (i.e., increase in severity). Medical events of interest, immune-mediated events, and AEs that occur more than 30 days after the last dose, and that are deemed as related to the study drug, will be included as TEAEs. TEAEs occurring from the time of the first dose through 30 days after the last dose of the study drug and medical events of interest, immune-mediated events and related AEs will be summarized. All AEs will be coded using the Medical Dictionary for Regulatory Affairs® (MedDRA v20.0 or newer). TEAEs will be tabulated by system organ class, preferred term, by treatment, and will be further categorized by NCI-CTCAE (v4.03 or newer) grade, and by relationship to the study drug. Clinically significant laboratory abnormalities, as measured by either the local or central laboratory, will be reported as AEs. The incidence for each AE will be provided as the total number of subjects that experience the AE, as well as the percentage of the population that this represents. If an AE is reported more than once during treatment for a given subject, the worst grade of severity and the most conservative relationship will be presented in the summary tables.

AEs will also be listed for individual subjects, along with information regarding onset, duration, grade, relationship to the study drug, and outcome. AEs that lead to withdrawal from the study treatment will be listed and summarized. Tabulations and listings of SAEs and deaths also will be generated.

Treatment exposure will be provided by treatment arm. The number of CMB305 or placebo injections, duration of exposure, and number of subjects with dose reductions/interruptions will be summarized by treatment arm based on the Safety set.

Laboratory values measured by the central laboratory will be used in the analysis of laboratory toxicities and will be defined based on universal normal ranges and NCI-CTCAE, Version 4.03 or newer. The number and percentage of subjects will be summarized by grade using the most severe grade by treatment arm. Clinically significant changes in laboratory values will be summarized by treatment arm. Laboratory values will be listed, with grade 3 or 4 values flagged.

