**Figure 1 CMB305 or Matching Placebo Dosing Regimen**

LV305 or matching placebo is administered as 4 separate 1-mL SC on Days 1, 22, 50, and 78, each preferably administered in a separate upper or lower limb (or stump if the subject has had a resection), or administered at least 3 cm from the neighboring injection site if on the same limb/stump.

G305 or matching placebo is administered IM on Days 36, 64, and 92, and then at 8-week intervals up to 1 year or until investigator-determined PD (using RECIST v1.1) is documented or unacceptable toxicity, whichever occurs first..

Three placebos (fully matched to characteristics of LV305, the NY-ESO-1 protein, and GLA-SE) will be provided for this study and will be administered on the same schedule and by the same route as the corresponding experimental therapy components to ensure that the sponsor, site personnel (including pharmacist), and subjects remain blinded to study drug for the duration of the study.

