## 4 SAMPLE SIZE DETERMINATION

A total of 248 subjects will be randomly assigned in a 1:1 ratio such that 124 subjects will be included in each of the 2 treatment arms. The study is powered at 90% with 179 death events required to detect a HR of 0.59, which corresponds to a 41% reduction in the risk of death, and an approximately 69% increase in median survival compared with a placebo median survival of 20 months, and uses a 1-sided log-rank test, with an alpha of 0.0125, a 1:1 randomization ratio, and an interim OS non-binding futility analysis with boundary of HR = 1.0 at 67% of information time (120 death events from the 179 required death events for the final OS analysis). A total of 248 subjects will yield the 179 events required, under the assumption of 24 months for enrollment (25% of subjects enrolled in the first year and 75% of subjects enrolled in the second year) plus 42 additional months of follow-up.

With 141 PFS events, the study is powered at 90% to detect a HR of 0.55, which corresponds to a 45% reduction in the risk of PFS events (either disease progression or death), and an approximately 82% increase in median PFS compared with a placebo median PFS of 4 months, and uses a 1-sided log-rank test, with an alpha of 0.0125, and a 1:1 randomization ratio.

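### Adverse events are compared by crude percentages only, although time at risk depends on PFS; exposure-adjusted rates should stand beside them

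*SAP*

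**What the plan says.** - **Summary measure.** SAP 8.3.1: "TEAEs will be summarized by presenting the number and percentage of subjects having at least one TEAE in each system organ class and preferred term". Protocol 7.8 likewise gives the count of subjects with each AE "as well as the percentage of the population that this represents".
- **Counting window.** SAP 5.2.1 counts AEs that appear or worsen "following initiation of the study treatment administration until 30 days after last dose of the study treatment". It adds treatment-related AEs with no time limit. Protocol 7.8 and SAP 8.3.1 also bring in medical events of interest (MEOIs) and immune-mediated events.
- **Dosing.** SAP 3.1.2 (text under Figure 1) has G305 or its placebo given every 8 weeks "up to 1 year or until investigator-determined PD (using RECIST v1.1) is documented or unacceptable toxicity, whichever occurs first". Protocol 6.5.2 also requires study drug to stop at RECIST progression, but then lets subjects who meet a list of conditions continue. These statements conflict.
- **Exposure.** SAP 8.3.6 defines duration of exposure and tabulates it by arm. It is not the denominator of any AE table. Neither document plans a person-time rate, a time-to-first-AE analysis or a common fixed window.
- **Role of the comparison.** Safety against placebo is a secondary objective (Protocol 2.2, SAP 2.2). No between-arm test of AEs is planned.

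**The concern.** Time at risk for a counted AE runs from first dose to 30 days after last dose. For a subject who stops at progression, that length is set by PFS. If CMB305 has no effect on PFS, both arms are observed for about the same time and crude percentages are a fair comparison. If CMB305 delays progression as the design assumes, its subjects are observed longer, and an AE that accrues steadily will be seen in more of them even when its rate is the same in both arms. A reader of the planned tables could not separate that excess from real toxicity. An adjustment chosen after unblinding would look post hoc.

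**Working it through.** **Inputs (SAP 4).** "With 141 PFS events, the study is powered at 90% to detect a HR of 0.55"; an "82% increase in median PFS compared with a placebo median PFS of 4 months"; the design "uses a 1-sided log-rank test, with an alpha of 0.0125". "A total of 248 subjects will be randomly assigned in a 1:1 ratio", so 124 per arm.

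**1. Reproduce the plan's figure.** Schoenfeld's formula gives 4 × (2.2414 + 1.2816)² / (ln 0.55)² = 4 × 12.411 / 0.3574 = 138.9, or 139 events against the stated 141. Power at 141 events is 90.5%. The PFS inputs are coherent.

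**2. Mean time at risk.** Take exponential PFS with hazards λ = ln 2 / 4 = 0.1733 per month (placebo) and 0.55 × 0.1733 = 0.0953 (CMB305, median 4 / 0.55 = 7.27 months). Dosing stops at progression or 12 months.

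Mean dosing time = (1 − e^(−12λ)) / λ = 5.05 months (placebo) and 7.15 months (CMB305).

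Adding w = 30 / 30.4375 = 0.99 months gives 6.04 and 8.13 months, a ratio of **1.35**.

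Variants:
- Last actual dose day before progression, plus 30 days: 5.32 vs 7.16 months, ratio 1.35.
- Progression seen only at the next 8-week scan: 6.87 vs 8.77 months, ratio **1.28**.
- Dose days and scan timing together: 6.17 vs 7.81 months, ratio 1.27.

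**3. Crude percentages at equal, constant AE rates.** The documents supply no AE rate, so the rate a per month is varied. With T = min(PFS, 12) + w,

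P(at least one AE) = 1 − e^(−aw) × [λ/(λ+a) × (1 − e^(−12(λ+a))) + e^(−12(λ+a))].

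Solving for the a that gives each placebo percentage:

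| Placebo | CMB305 | Ratio |
|---|---|---|
| 5% | 6.7% | 1.34 |
| 10% | 13.3% | 1.33 |
| 25% | 32.3% | 1.29 |
| 40% | 49.9% | 1.25 |
| 50% | 60.7% | 1.21 |
| 80% | 87.2% | 1.09 |
| 90% | 94.0% | 1.04 |

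For very rare AEs the ratio tends to the time-at-risk ratio, 1.35. With dose days and 8-week detection the ratios are smaller: 1.25 at 10%, 1.20 at 40%, 1.08 at 80%. A rate per person-month would have a ratio of 1.00 throughout.

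**4. AEs confined to Days 1 to 92.** Let the rate be a up to Day 92 (91 / 30.4375 = 2.99 months), zero afterwards, and equal in both arms. With b = min(T, 2.99), the crude percentage is E[1 − e^(−ab)]. Person-time censored at first event is E[(1 − e^(−ab))/a + e^(−ab)(T − b)].

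- a = 0.05: crude 12.5% vs 13.1% (ratio 1.05); rate 2.32 vs 1.82 per 100 person-months (ratio 0.78).
- a = 0.40: crude 64.7% vs 66.9% (ratio 1.03); rate 24.6 vs 20.4 (ratio 0.83).
- a = 0.40, progression seen only at scans: crude ratio 1.00, rate ratio 0.84.

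Here the crude percentages are nearly fair. The person-time rate is misleading in favour of CMB305, because its extra late months carry no events. If the early period is extended by the 30-day tail, the crude ratio is 1.06 to 1.08.

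**The case against.** - **The regimen is front-loaded.** Seven of eleven scheduled dose days fall by Day 92, including all LV305 injections. Under the same PFS assumptions, mean dosing visits per subject are 6.5 vs 8.0 (ratio 1.23), or 7.6 vs 8.7 (1.15) with scan-based detection. AEs driven by each dose would be less unbalanced than time at risk suggests. This stands, and it is why the size is given as a range.
- **Rates can mislead in the other direction.** Step 4 shows this. A reader might conclude that between-arm statements should rest on the adjusted rates; the regimen does not support that.
- **The consequence is limited.** The tables are descriptive, exposure is tabulated by arm, AE onset is listed by subject, and the distortion overstates CMB305 toxicity and does not hide it. All true, and all reasons to treat this as an improvement and not a flaw in the trial's conclusions. It does not answer the case for fixing the calculation in advance.
- **Dosing does not always stop at progression.** Protocol 6.5.2 allows continuation, and the documents do not say how often it would happen. Stopping for toxicity or withdrawal has no stated rate either. The ratio could move by an amount that cannot be fixed from the documents.

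A reader might also infer that CMB305 will show 24% to 32% more subjects with an AE. Those figures arise only for constant rates of 0.02 to 0.10 per month (11.1% vs 14.7%, 24.7% vs 31.8%, 41.3% vs 51.3%). The documents give no such rates, and the figures do not hold for very common or early AEs.

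**Conclusion.** The point holds in conditional form. The AE tables use crude percentages alone, while time at risk is tied to a primary endpoint. Under the design PFS assumptions, mean time at risk is about 28% to 35% longer on CMB305, before any dosing past progression or stopping for toxicity or withdrawal. At equal constant AE rates the relative excess in crude percentages runs from about 35% for rare AEs to about 4% for an AE seen in 90% of placebo subjects, and is almost nil for AEs confined to Days 1 to 92. It rests on exponential PFS, the planned hazard ratio and an assumed AE pattern. It does not follow that the safety comparison is distorted whenever the trial succeeds, because for early AEs the crude percentages remain nearly fair. This is a low-cost improvement to the safety reporting.

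**What to change.** In SAP 8.3.1, add exposure-adjusted first-event rates per 100 person-months, by arm, beside the crude percentages for all TEAEs, Grade 3 or higher TEAEs, SAEs, related TEAEs and MEOIs. Define person-time as first dose to last dose + 30 days, censored at first event, death or data cutoff. Count only events with onset in that window in the rates; later related AEs and MEOIs stay in the crude tables as planned. State that the two measures are read together, that between-arm statements do not rest on the rates alone, and that the crude percentages remain the measure for early events.

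Separately, the stop-at-progression wording in SAP 3.1.2 and Protocol 5.2 and the continuation wording in Protocol 6.5.2 must be reconciled, since they determine time at risk.

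The cost is a few extra table columns from dose and onset dates already collected. The downside is that the rates assume a roughly constant hazard and would favour CMB305 for front-loaded AEs, as step 4 shows, so the SAP should carry that caution with the tables.
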